5.6 Data Analysis

Sample size calculations were determined using Stata statistical software.²⁷ The study is powered for the overall omnibus F test used in the Fisher protected least significant difference test. The study is also powered for the ability to detect at least a moderate effect size between each pairwise sub-test (MBSR/usual care, CBT-CP/usual care, and as an exploratory aim MBSR/CBT-CP), which will be performed if the omnibus test is significant. The study is powered to detect a difference of Cohen's $d \geq 0.50$ between treatment arms (which represents a change of 1.05 points on the BPI pain interference subscale, based on data from Veterans with chronic pain).²⁸ Sample size calculations for the omnibus ANOVA

assume a 1:1:1 treatment allocation, desired power of 80%, 2-tailed $\alpha = 0.05$, and estimate that BPI pain interference scores will be 1.05 points lower in both the MBSR and CBT-CP arms compared to usual care (using a SD=2.1 for BPI scores).²⁸ Using these parameters, 59 patients per arm of the study are needed (N=177). The sample size was inflated to 222 to account for possible attrition. Sample size estimates for comparisons between subtests (e.g., MBSR/usual care, CBT-CP/usual care) were also calculated using t-tests. For a desired power of 80% and a 2-tailed $\alpha = 0.05$, 64 patients for each of the three arms of the study are required (N = 192). Further inflation of this sample size by 15% to account for attrition or the effects of clustering resulted in a total of 222 patients. Detecting an effect size of Cohen's $d \geq 0.50$ has been advocated as a reasonable threshold of clinical significance when assessing patient reported outcomes, including pain and physical and emotional functioning.²⁹ In our pilot study of MBSR for Veterans with Gulf War illness (preliminary studies) the intraclass correlation for measures of pain was $p= 0.00$ at follow-up, indicating that we likely do not need to account for clustering in our sample size estimates. To provide 80% power if $ICC = 0.02$ is found, inflation of the sample size by 6% would be required; the inflation of the sample size by 15% was performed as a conservative measure to account for possible clustering or attrition. The sample size required per arm of the study for treatment comparison (at 80% and 90% power) is presented across a range of effect sizes in Table 2.

Table 2. Effect size (d)	two-tailed $\alpha = 0.05$, $\beta = 0.20$	two-tailed $\alpha = 0.05$, $\beta = 0.10$
0.40	100	133
0.50	64	86
0.60	45	60
0.70	34	44

Data will be analyzed following the completion of the final assessments of the last subject cohort, which is projected to take place in the last six months of Year Three of the study. The dataset will be analyzed by [name].

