Measures pertaining to the primary outcome of pain interference will be collected at baseline, at the post-MBSR/CBT-CP time point, and at 6-month post treatment follow-up. In addition, measures of pain intensity, depression, and treatment satisfaction will be applied to more fully characterize the impact of MBSR relative to CBT-CP and usual care. Exploratory analyses will assess if outcomes differ for MBSR and CBT-CP, the impact of the interventions on opioid use and indicators of suicidality, and whether Veteran characteristics assessed at baseline function as treatment moderators. Mixed models will assess whether MBSR, CBT-CP each produce greater reductions in outcome variables from baseline to follow-up compared to usual care. If MBSR and CBT-CP are each shown to be superior to usual care for treatment of chronic pain among Veterans, it would support providing MBSR and CBT-CP for this population.

List of Abbreviations

MBSR – Mindfulness-Based Stress Reduction

CBT-CP – Cognitive Behavioral Therapy for Chronic Pain

CPRS – Computerized Patient Record System (electronic medical record)

PROMIS – Patient-reported Outcome Measures Information System

TAU- Treatment as Usual

VVC- VA Video Connect technology (telehealth video portal)

Contents

Protocol Title:	4
1.0 Study Personnel	4
2.0 Introduction	4
3.0 Objectives	4
4.0 Resources and Personnel	8
5.0 Study Procedures	9
5.1 Study Design	10
5.2 Recruitment Methods	13
5.3 Informed Consent Procedures	15
5.4 Inclusion/Exclusion Criteria	16
5.5 Study Evaluations	17
5.6 Data Analysis	19
5.7 Withdrawal of Subjects	20
6.0 Reporting	21
7.0 Privacy and Confidentiality	22
8.0 Communication Plan	22
9.0 Information Security and Data Storage/Movement	23
10.0 References	9

Protocol Title: A Randomized Clinical Trial of Group Interventions Compared to Usual Care for Veterans with Chronic Musculoskeletal Pain

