3.0 Objectives

The Primary Aim of this study is to determine whether MBSR and CBT-CP each result in greater reductions in the pain interference subscale of the Brief Pain Inventory (BPI) as compared to usual care, from baseline to 6 months post-treatment for Veterans with Chronic Musculoskeletal Pain.

Hypothesis: Veterans with chronic pain randomized to each active intervention (MBSR or CBT-CP) will report changes in BPI pain interference that are each superior to usual care, from baseline to 6-month follow-up.

Secondary Aim: Evaluate if MBSR and CBT-CP are each superior to usual care in producing improvements in pain severity, treatment satisfaction, and depression. **Exploratory Aim 1:** Evaluate whether outcomes for patients randomized to MBSR and CBT-CP differ for changes in pain interference, pain severity, depression, and treatment satisfaction. **Exploratory Aim 2:** Evaluate the impact of MBSR and CBT-CP on utilization of opioid analgesics and markers of suicidality. **Exploratory Aim 3:** Evaluate moderators of response to MBSR and CBT-CP to lay the groundwork for identifying Veterans more likely to succeed in one or the other treatment. Potential moderators assessed will include: age,

gender, baseline depressive symptoms, anxiety sensitivity, and pain catastrophizing

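### The 80% power for each pairwise comparison (64 per arm) leaves out the requirement that the omnibus F test be significant first; under the planned procedure it is about 76%

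*Combined protocol and SAP*

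**What the plan says.** Section 5.6 (Data Analysis) names Fisher's protected least significant difference procedure and gives two separate power calculations. The omnibus test, with both active arms 1.05 points below usual care and SD 2.1, needs 59 per arm for 80% power. For the pairwise comparisons the section states: "The study is also powered for the ability to detect at least a moderate effect size between each pairwise sub-test". It adds that these are tests "which will be performed if the omnibus test is significant". The pairwise figure comes from t-tests at two-sided 0.05 and 80% power: "64 patients for each of the three arms of the study are required (N = 192"). Table 2 extends this calculation to other effect sizes and to 90% power.

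The total of 192 is then raised by 15%, for attrition or clustering, to 222 (74 per arm). On clustering, the section says that if the ICC were 0.02, "inflation of the sample size by 6% would be required".

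Section 3.0 (Objectives) states the hypothesis for each treatment separately: the active arms "will report changes in BPI pain interference that are each superior to usual care, from baseline to 6-month follow-up". The Abstract makes its planned conclusion depend on both: "If MBSR and CBT-CP are each shown to be superior to usual care for treatment of chronic pain among Veterans".

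**The concern.** A t-test calculation gives the chance that one comparison is significant when it is always carried out. Here it is carried out only after a significant F test. The two events overlap heavily but not completely: some data sets with a significant pairwise difference have a non-significant F. The chance of showing a given treatment superior is therefore below the t-test figure, and neither section 5.6 nor Table 2 says so. Since the primary aim is each treatment against usual care, this joint event is what decides it.

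Two things are at stake. The stated power is too favourable for the declared procedure at the sample size called required. The room for attrition also looks larger than it is, because the 15% inflation starts from 64 and is already assigned to attrition or clustering.

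**Working it through.** **Inputs, all from section 5.6.** Three arms, 1:1:1; difference 1.05 points in both active arms; SD 2.1, so d = 1.05/2.1 = 0.50; two-sided alpha 0.05; omnibus F test first, then pairwise tests.

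**Reproducing the plan's figures.**
- Pairwise t-test: noncentrality d·√(n/2). At n = 64 this is 0.50 × √32 = 2.83 with 126 df, giving power 80.1% (79.5% at n = 63). The plan's 64 is right.
- Omnibus F: standardised means 0, 0.5, 0.5 have mean 1/3 and squared deviations 1/9 + 1/36 + 1/36 = 1/6, so λ = n/6. At n = 59, λ = 9.83 and power is 80.1%. The plan's 59 is right.
- All eight entries of Table 2 reproduce from the noncentral t.

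**Power under the planned procedure.** The quantity needed is P(omnibus F significant and the named comparison with usual care significant), called protected power below. It was simulated with three normal groups, the pooled three-group variance, F at 0.05 and then t at two-sided 0.05, with 2,000,000 trials per setting. The Monte Carlo standard error is about √(0.76 × 0.24/2,000,000) = 0.03 percentage points.

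| Evaluable per arm | Omnibus | Pairwise alone | Protected, one named comparison | Protected, both comparisons |
|---|---|---|---|---|
| 59 | 80.1% | 77.0% | 72.1% | 64.1% |
| 63 | 82.9% | 79.7% | 75.3% | 67.7% |
| 64 | 83.5% | 80.4% | 76.1% | 68.6% |
| 70 | 86.9% | 83.8% | 80.2% | 73.5% |
| 74 | 88.8% | 85.8% | 82.6% | 76.4% |

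At 69 per arm protected power is 79.5%, so 70 is the smallest number that reaches 80%. Using separate two-sample t-tests after the F test instead of the pooled variance gives 75.9% at 64, essentially the same.

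**Effect size needed at 64 per arm.** Protected power is 79.6% at d = 0.52 and 80.5% at d = 0.525, so 80% needs d of about 0.52, or roughly 1.10 points.

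**Table 2 under the procedure, both active arms at the tabulated d.** For d = 0.40, 0.50, 0.60, 0.70 the 80% column gives 76.2%, 76.1%, 76.4%, 77.5%; the 90% column gives 88.0%, 88.4%, 88.4%, 88.2%.

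**Attrition margin.** If 64 were enough, 1 − 64/74 = 13.5% could be lost. With 70 needed, 1 − 70/74 = 5.4%. A 15% loss leaves 74 × 0.85 = 62.9, about 63 per arm, with protected power 75%. If the plan's 6% for ICC = 0.02 applied, 70 × 1.06 = 74.2, which uses up the whole enrolment.

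**If the other arm differs from the plan's assumption.** At 64 per arm, protected power for the arm with d = 0.50 is 76% when the other arm also has 0.50, 73% at 0.40, 70% at 0.25, 73% at 0.10 and 76% at 0. The low point comes where the other arm lies midway: the squared deviations then sum to 0.125 instead of 1/6, λ falls from 10.67 to 8 and omnibus power drops to 71%.

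**Both treatments superior.** At 64 per arm this is 69.3% without the omnibus condition and 68.6% with it. This figure therefore comes almost entirely from requiring both comparisons.

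**The case against.** The best defence is that no printed number is wrong. The plan says the pairwise figures come from t-tests, gives the omnibus calculation separately and states the condition in the same paragraph. Moreover, 74 per arm are randomised, and at 74 evaluable the protected power is about 83%. The documents give no expected attrition rate, and the pilot ICC was 0.00, so clustering may cost nothing.

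Much of this stands as a limit on the point. The 76% belongs to 64 evaluable per arm, and the ICC = 0.02 case is a contingency that the plan thinks unlikely. But 64 is the number the plan itself ties to 80%, and counting the 15% on top as a reserve for power spends it twice.

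A second objection is that a single-score ANOVA is not the planned analysis, since the Abstract says: "Mixed models will assess whether MBSR, CBT-CP each produce greater reductions in outcome variables from baseline to follow-up compared to usual care". That is fair. Section 5.6 takes no credit for this and gives no correlation r between baseline and follow-up, so the effect can only be shown by assumption. At 64 per arm with baseline adjustment, protected power is 76.1% at r = 0, 80.3% at r = 0.3 and 87.9% at r = 0.5. With unadjusted change scores it is 59.5% at r = 0.3, 76.0% at r = 0.5 and 94.3% at r = 0.7. The choice of model can thus matter more than the omnibus condition, in either direction, but in each case protected power is below the stand-alone figure for the same model.

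Finally, section 5.6 never claims power for both treatments jointly, so the 69% marks an omission and not an error in a stated figure. The unequal-effect results are sensitivities outside the plan's scenario.

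**Conclusion.** The concern holds. At the sample size the plan calls required, its own testing procedure gives about 76% power per comparison with usual care, some 4 percentage points below the stated 80%. This rests on the plan's single-score ANOVA model, equal effects of 1.05 points in both active arms, SD 2.1, no clustering and 64 evaluable per arm. The shortfall disappears if at least 70 per arm are evaluable. It is a modest discrepancy that should be corrected; it does not undermine the design.

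**What to change.** Keep N = 222 and the testing procedure. In section 5.6, label the 64 per arm at 80%, and Table 2, as the power of a single two-sample t-test that does not depend on the omnibus result. Then add, for example:

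> Under the same simple ANOVA model (both active arms 1.05 points lower, SD 2.1, no baseline adjustment, no clustering), 64 evaluable patients per arm give about 83% power for the omnibus test, about 76% for each comparison with usual care when a significant omnibus test is also required, and about 69% for both comparisons. Power of 80% for each comparison under this procedure needs 70 evaluable per arm.

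If the sponsor prefers to state power under the planned mixed model, it should give the model and the baseline-to-follow-up correlation assumed.

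The cost is two or three sentences and a table label, with no extra patients and no change of test or endpoint. The only drawback is a slightly less favourable stated power.

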A meta-analysis of acceptance-based approaches for chronic pain found medium effects for pain intensity ($d=0.48$).¹⁴ Another review of 16 trials of MBIs showed reductions in pain intensity in 6 of 8 randomized controlled trials (RCTs), with medium effect sizes.¹² Furthermore, when analyses were limited to samples involving clinical pain, 9 of 11 studies showed reductions in pain intensity.¹² There have been few comparisons of MBSR to an active control. One non-randomized pilot study ($n=50$) compared MBSR to CBT and found a larger effect size in favor of MBSR ($d=0.87$).¹⁶ Another non-randomized study ($n=58$) compared MBSR to a social support group and found medium effects in favor of MBSR for sensory/affective pain, and large effects ($d=1.10$) using a pain visual analogue scale.¹⁷ The findings of prior pilots – subject to the limitations of small sample sizes – are generally consistent with the data from our small pilot study among GW Veterans ($n=55$), which showed greater reductions in pain severity after MBSR as compared to usual care ($d=0.66$).

One mechanism hypothesized to account for reduced pain is that enhanced mindfulness leads to ‘uncoupling’ of the cognitive and emotional elements from the sensory experience of chronic pain, which results in decreased distress and suffering¹⁸; it has been proposed that the affective component of pain can be distinguished from pain intensity, and that the affective component can be differentially targeted¹⁹. Data from both correlational and experimental studies performed in chronic pain populations suggest that enhanced mindfulness is associated with reduced pain intensity ratings.^{12,20,21} Studies of healthy volunteers also support reduced pain intensity associated with MBIs. One study found that three days of mindfulness meditation training led to reduced pain intensity ratings following electrical stimuli²² and another study showed that three days of mindfulness training was superior to guided imagery in increasing pain tolerance to the cold pressor test.²² Other research has found that anxiety decreases pain threshold and lowers pain tolerance.²³ Thus, interventions that reduce anxiety would be expected to lead to reductions in pain severity.

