5.0 Study Procedures

5.1 Study Design

The proposed study is a three-arm comparative effectiveness trial that will randomly assign Veterans with chronic musculoskeletal pain to MBSR, CBT for chronic pain (CBT-CP) or usual care to assess the effectiveness of MBSR or CBT-CP for Veterans with chronic musculoskeletal pain. Veterans with chronic

musculoskeletal pain (N =222) will be randomized to either 8 weeks of MBSR (n =74), 8 weeks of CBT-CP (n =74) or usual care (n=74), and will complete assessments at baseline, immediately post-treatment and at 6-month post-treatment. Randomization will be performed through REDCap, and stratified by sex assigned at birth and pain severity score. Sessions will be audio recorded using both Philips DPM 8000 recorders and OBS Studio software. Fidelity coding from audio recordings will evaluate protocol adherence for both MBSR and CBT-CP.

A comprehensive outline of the various data collection tools/measured to be administered at each of the three assessments is provided in **Section 5.5 Study Evaluations**.

Risk and Benefit: The risks for this study involve the potential for psychological distress associated with collection of self-report data, and the possibility that undergoing either the MBSR class or CBT-CP could be stressful and worsen symptoms. There is also a risk of confidentiality due to the group nature of MBSR and of CBT-CP, and the delivery of these groups by the VVC internet based platform; those who are unwilling to be in an MBSR class or CBT-CP group that is being audiotaped will need to seek other services. Further, there is a risk that MBSR and CBT-CP will not be efficacious for some individuals. We plan to educate patients about the possible risks and benefits prior to study enrollment by providing a thorough orientation to the research and an overview of each intervention prior to giving informed consent. Potential benefits for those randomized to either condition may take the form of reduced chronic musculoskeletal pain symptoms, and increased health-related quality of life. Veterans' families may also benefit as a result of the shift in emotional state. However, a participant may not benefit directly from participation in the study. Information gained in the study may be of benefit in the future to persons with chronic musculoskeletal pain. Specific measures for minimizing risk are outlined below.

Procedures to Minimize Risk to Subjects and Protect Confidentiality:

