5.7 Withdrawal of Subjects

If the study subject becomes a threat to the safety of others in his or her treatment group, or to the research team, that subject's participation in the study will be terminated, and they will be withdrawn from the research without their consent.

If a study subject demonstrates behavior that repeatedly violates the community guidelines of their treatment group, so much so that they actively prevent the group from being able to achieve the day's curriculum or they create a hostile environment for other group members or research staff, that subject's participation in the groups will be terminated, and the PIs will determine if they can continue to participate in the study and complete the research assessments with study staff.

If a subject wishes to withdraw from the study before all procedures are complete, he or she simply needs to notify the study's project manager, study coordinator, or other study team member by phone or in person that he or she no longer wishes to participate, and the subject will be withdrawn from the study and no longer contacted regarding study procedures. A primary study contact number will be provided to each participant, so they know how to reach the study team to request early withdrawal (or for any other questions).

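### The analyses named contain no therapy-group term for the two group-delivered arms; if it is left out and outcomes correlate within groups, the primary omnibus test rejects somewhat too often

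*Combined protocol and SAP*

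**What the plan says.** Both active treatments are group treatments. Section 5.1 warns: "There is also a risk of confidentiality due to the group nature of MBSR and of CBT-CP". Section 5.7 has a withdrawal rule that begins "If the study subject becomes a threat to the safety of others in his or her treatment group". No groups are described for usual care.

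Two descriptions of the analysis are given. The Abstract names mixed models for change from baseline to follow-up and states no random effects. Section 5.6 says "The study is powered for the overall omnibus F test used in the Fisher protected least significant difference test", with pairwise comparisons to follow if that test is significant, and it sizes those comparisons with t-tests.

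Clustering appears only in the sample-size text of 5.6. The evidence is introduced with "In our pilot study of MBSR for Veterans with Gulf War illness (preliminary studies) the intraclass correlation for measures of pain", reported as 0.00 at follow-up, "indicating that we likely do not need to account for clustering in our sample size estimates". For an ICC of 0.02, 5.6 says that "inflation of the sample size by 6% would be required" to keep 80% power, and adds that "the inflation of the sample size by 15% was performed as a conservative measure to account for possible clustering or attrition".

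**The concern.** Patients who share a therapy group share an instructor, a schedule and each other, so their outcomes may be correlated. A model without a group term treats them as independent and understates the variance of the two active-arm means. The omnibus F test for pain interference, which opens the way to the pairwise comparisons with usual care, would then reject more often than its nominal 5%.

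A larger sample does not repair this. For a given group size and ICC, the ratio of the true to the assumed variance is the same at 64 or 74 per arm.

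Because the random effects are unstated, the choice could also be made after the data are seen, and it affects significance.

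**Working it through.** **Plan's own figures.** With means 0, −1.05, −1.05 and SD 2.1, the noncentral F gives 80.1% power at 59 per arm. The noncentral t at d = 0.50 needs 64 per arm. Then 64 × 1.15 = 73.6, so 74 per arm and 222 in total. These all reproduce.

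**Group size behind the 6%.** The text reviewed gives no group size. The design effect is DE = 1 + (m − 1) × ICC, where m is patients per group. At ICC 0.02:
- full design effect applied: 1 + 0.02(m − 1) = 1.06, so m = 4;
- averaged with an unclustered usual-care arm: [1 + 1 + 0.02(m − 1)]/2 = 1.06, so m = 7.

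Groups of 4–7 are therefore implied by the plan. Groups of 10–12 are my assumption, to show the range.

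**Understated standard error, active arm versus usual care.** With equal arms the true variance is (1 + DE)/2 times the assumed one. For a single unprotected comparison, the two-sided error is about 2 × [1 − Φ(1.96/√ratio)]:

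| m (ICC 0.02) | DE | Variance ratio | SE ratio | Approximate error |
|---|---|---|---|---|
| 4 | 1.06 | 1.03 | 1.015 | 5.4% |
| 7 | 1.12 | 1.06 | 1.030 | 5.7% |
| 10 | 1.18 | 1.09 | 1.044 | 6.1% |
| 12 | 1.22 | 1.11 | 1.054 | 6.3% |

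**Full procedure, by simulation.** Single follow-up score, total SD 1, 74 in usual care, 70–74 per active arm in equal or nearly equal groups, pooled F test at 5%, then LSD, no group term. Independent runs differ by about 0.2 points.

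| Error rate | Groups of 4 | Groups of 7 | Groups of 10–12 |
|---|---|---|---|
| ICC 0.02: omnibus, neither arm works | about 5.6% | about 6.3% | about 7% |
| ICC 0.02: any false claim against usual care, neither arm works | about 4.6% | about 5.0% | 5.5–6.1% |
| ICC 0.02: false claim for one arm when only the other works (d = 0.5) | about 5.3% | about 5.7% | 5.7–6.3% |
| ICC 0.05 (not in the documents): omnibus | about 6.5% | about 8.2% | about 10–11% |

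The third row agrees with the formula above, as it should: once the other arm works, the omnibus test usually passes and gives little protection. At ICC 0 the omnibus error is 5%.

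**With the group term** (REML, one group variance shared by the active arms and held at or above zero, Satterthwaite degrees of freedom; groups of 7–12): omnibus error is 4.0–4.2% at ICC 0.02 and 3.4–3.8% at ICC 0. It is controlled, and slightly conservative.

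**The case against.** The plan is silent rather than wrong, and parts of it point towards clustering being modelled. Section 5.6 speaks of an ICC of 0.02 being found, which suggests that it will be estimated. An allowance to preserve power makes most sense if the analysis accounts for groups, and mixed models can carry a group term. Some text, including the preliminary studies to which 5.6 refers, was not in the copy reviewed. All this stands: a reader might infer that the plan intends to ignore groups, and the documents do not support that. But mixed models described for change over time may mean only repeated measures, and an F test with LSD, run as named, has no group term.

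A reader might also infer serious inflation, with omnibus error of 8–11%. That needs an ICC such as 0.05 with groups of 7–12, and no document gives that ICC. Nor is the omnibus test itself the primary claim. With neither treatment working, at the group sizes the plan implies, the chance of a false claim against usual care is about nominal.

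The pilot ICC should be neither dismissed nor leaned on. It comes from MBSR, so for CBT-CP it is indirect evidence. The Introduction mentions "our small pilot study among GW Veterans ($n=55$), which showed greater reductions in pain severity after MBSR as compared to usual care"; if that is the same pilot, which is an inference, an estimate of 0.00 from so few patients says little about whether the ICC is 0 or 0.02.

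Finally, the term has a price. If the ICC is 0, it gives up power to correct an error that is not there. That is a fair point, and the cost is set out under the fix.

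**Conclusion.** The specification gap is real and its consequence is modest. The documents establish group delivery in two of three arms, no named group term, and an allowance for clustering in the sample size only. The harm is conditional on two things: the term being left out, and an ICC above zero. At the plan's ICC of 0.02, omnibus error for pain interference is then about 5.5–6.3% at 4–7 per group and about 7% at 10–12. False claims against usual care lie between about 4.5% and 6.3%, depending on group size and on whether the other arm works. The 4–7 is back-calculated from the plan's 6%; the larger groups are assumed. The gate is stated in the sizing text for pain interference, so I do not extend this to the secondary outcomes. It should be fixed as a cheap improvement in specification; it is not a threat to the trial's validity.

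**What to change.** In the primary mixed model, pre-specify:
- a random intercept for therapy group in the MBSR and CBT-CP arms only, none in usual care;
- one group variance shared by the two active arms (separate variances would leave fewer degrees of freedom);
- Kenward-Roger or Satterthwaite degrees of freedom;
- reporting of the estimated ICC.

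This takes one model term and one sentence. Group membership is known from delivery, so no new data are needed.

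The statistical cost, simulated for groups of 7–12 before attrition, is as follows. If the true ICC is 0, intervals against usual care are about 4–6% wider. If both arms work (d = 0.5), power for one active arm under the omnibus-first rule falls from about 82% to 79% (groups of 7) or 78% (groups of 12), slightly below the 80% target. If only one arm works, omnibus power falls from 87–88% to 82% or 80%. At ICC 0.02 intervals are 6–10% wider, of which 3–5% is the correction needed. The exploratory MBSR versus CBT-CP contrast may have as few as 18 (groups of 7) or 10 (groups of 12) degrees of freedom, which makes its intervals 7–13% wider.

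Do not enlarge the trial for this. Stating the group size behind the 6% in 5.6 would be a useful but optional clarification.
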